5.6.2 Instructions for prescribing and taking study treatment

Throughout the study, treatment (either secukinumab or placebo) will be administered subcutaneously either by the subject or by an approved individual. Prefilled syringes will be provided by the site staff to the subject. Initial injections will be performed at the site to train subjects in proper subcutaneous injection technique. Study personnel will perform first injection with subject observing, then subjects will use the second syringe to demonstrate the ability to inject themselves. After this instruction and observation, subjects will be able to self-administer weekly or monthly injections.

We will contact subjects weekly by phone/Skype/FaceTime (subjects will designate which is best) on weeks 1-3 to answer questions, assure adherence to administration, and ensure safety and return at week 4. Subjects will keep a diary of administration dates and times, which will be reviewed at each appointment. All subjects who receive at least one dosage will be counted in the ITT population.

Injections are to be administered at a different anatomic location (such as dominant upper arm, thigh, or any quadrant of the abdomen except for 2 inches around the navel area) than the previous injection. Subjects may not self-inject upper outer arm but this area may be used by caregiver or healthcare provider for injection. Injections should not be given in areas where the skin is tender, bruised, erythematous, or indurated if possible.

Product: Secukinumab

Protocol Number: CAIN457AUS05T

Date: 14 July 2018

24

5.6.3 Prohibited treatment

Subjects should not receive live vaccines during this study. They may not use any topical agent for the treatment of ichthyosis other than over the counter emollients. They may not be on any systemic agents for the treatment of ichthyosis. Subjects who experience skin infection requiring antibiotics during the study will not be discontinued from study drug or withdrawn from the study. The therapies they require will be noted by investigator on the case report form.

5.7 Subject Withdrawal/Discontinuation

Subjects will be evaluable if they complete all required assessments and visits through and including Week 16. If subjects fail to return for study visits, or become lost to follow up, subjects will be considered withdrawn. The PI and/or designated study staff will attempt to follow up with these individuals to discern the reason for their non-compliance. Similarly, if subjects choose to discontinue their participation in the study, study staff will attempt to contact the subject to determine their reason for discontinuation. The subject may also be discontinued by the PI for lack of efficacy.

Study treatment must be discontinued and the subject withdrawn if the investigator believes that continuation would compromise the subject's well-being. Treatment must be discontinued under the following circumstances:

- Occurrence of any AEs determined by the PI to prevent subject continuation with treatment
- Neutrophil count is less than 1000 or less than 1500 accompanied with fever
- Pregnancy
- Use of prohibited treatment
- Emergency unblinding

Subjects who discontinue study treatment will return at next scheduled visit to undergo an end of study visit and then be discontinued from the trial.

5.8 Study Completion and Post-study Treatment

Study participation is completed for the subject at the conclusion of their week 52 study visit. Adverse events that occur within 30 days of this visit must be documented and reported by the PI.

The study as a whole will be completed when all 40 randomized subjects have completed their 52 week treatment course as per the protocol and the complete data analysis, including limited gene expression analysis in skin has been performed.

Upon completion of their study participation, subjects will return to individual treatment, as determined by their regular treating physician.

6. VISIT SCHEDULE AND ASSESSMENTS

Appendix 1 lists the assessments and indicates with an "X" when the visits are performed. Subjects should be seen for all visits on the designated day or as close as possible to the original planned visit schedule (recommended visit windows are provided in Appendix 1). Special respect and effort for the baseline, week 8, week 16, week 32, and week 52 visits should be made.

Product: Secukinumab

Protocol Number: CAIN457AUS05T

Date: 14 July 2018

25

In the event that subjects do not present for their study visit, study staff will document their attempts to contact these individuals.

6.1 Screening Visit

The screening visit is to be performed within 21-28 days of baseline visit [day 0]. After providing informed consent, subjects will be assessed for study eligibility at the screening visit (day -28 to day -21), which includes blood tests, infection screening, assessment of vital signs, assessment of skin severity scores, genotyping, photography, skin swabs and scrapings, and pregnancy test (if applicable).

6.1.1 Consent

Consent will be obtained by the study investigator or by approved study staff at the screening visit (visit 1) as indicated in Appendix 1. All participants will be given time to read the pre-approved consent forms, and ask any questions they may have. The consentor will emphasize that the study is voluntary. Consent forms will be kept in a designated study office in a locked drawer.

6.1.2 Medical and Medication History

A PI or designated study staff member will collect information regarding relevant medical history/current medical conditions excluding ARCI-LI, ARCI-CIE, NS or EI at every study visit as indicated in Appendix 1. All collected information will be documented. When possible, diagnoses (rather than symptoms) will be recorded. The history regarding ARCI-CIE, ARCI-LI, NS or EI will also be obtained including date of diagnosis and prior treatments. Medications including current medications and those taken within six months preceding enrollment will be recorded. Particular attention must be paid to any history of joint pain and IBD (history of diarrhea/constipation, bloody/painful stool, increased gas/bloating). Attention should also be paid to current treatments for ichthyosis (including bleach baths, any recent topical or systemic antibiotic use, skin care regimen and use of any topical or systemic medication).

6.1.3 Vital Signs and Height

Vital signs, including blood pressure, pulse, respiratory rate, temperature, weight will be collected at every study visit for all subjects as indicated in Appendix 1. Height will be recorded at the first visit as indicated in Appendix 1.

6.1.4 Complete Physical Examination

A complete physical examination will be performed by a physician or a qualified, licensed healthcare professional. A full examination will occur at the screening and baseline visits, as well as Weeks 16, 32, and 52; a full skin exam including measurement of TEWL will occur at visits 2-12 as indicated in Appendix 1. TEWL will be measured at upper outer arm near biopsy site and upper buttock. Waist circumference will be measured at baseline, weeks 16, 32, and 52. Additional exam components and maneuvers may be necessary depending on presenting symptomatology and are at the discretion of the PI or study staff. Results will be documented in the Medical History if present before signing the informed consent. If examination shows abnormal findings that meet criteria for an AE after the informed consent form has been signed and the subject has been enrolled with study drug initiation, these findings will be documented as such in the subject's file.

Product: Secukinumab

Protocol Number: CAIN457AUS05T

Date: 14 July 2018

26

6.1.5 Genotyping & Genetic testing

At Northwestern University, all patients must either have known genotype available to the investigator or agree to be separately consented to undergo saliva-based DNA testing as offered at no cost by [name] at Yale on a research basis; the investigator will know the mutated gene, but not the exact mutation and will be able to report this information to the subject. Consent will be per Lurie Children's Hospital Institutional Review Board-approved project STU00202786 under [name]. Sampling for [name] will be performed by saliva collection.

At Mt. Sinai, subjects' genotype information will be collected only if already available (i.e. subject can provide documentation).

In addition, buccal swabs will be collected at screening visit for banking (e.g., potential pharmacogenomics) at both sites.

6.1.6 Infectious Disease Testing

Testing for HIV, hepatitis B and C, and quantiferon gold testing for tuberculosis (TB) will be performed at the site of screening (Northwestern or Mt. Sinai) for all subjects at visit 1 as indicated in Appendix 1. A blood draw by a trained phlebotomist will be necessary for HIV, hepatitis B and C testing. Subjects must have negative testing for all infectious diseases tested to be randomized. If the subject has an indeterminate QuantiFERON®-TB gold, the test may be repeated once. If the result is positive or remains indeterminate, the subject may not participate in the study. Patients will be referred for any positive or indeterminate result to an appropriate physician for management. If the subject has been treated in the past for active or latent TB, they will be excluded from the study.

Should there be suspicion of an infectious complication (such a bacterial or fungal/candida infection), the area will be photographed for documentation, and infection confirmed by culture as appropriate.

6.1.7 Pregnancy Testing

All female study subjects will be tested for pregnancy at the baseline and end study visits as indicated in Appendix 1. Urine HCG testing will be obtained. Any woman with a confirmed positive pregnancy test during screening is not eligible for randomization and participation in this study.

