4.1 Inclusion Criteria

Subjects are qualified for enrollment if they meet the following criteria:

- Subject has provided informed consent
- Subjects are at least 18 years of age or older at the time of screening.
- Female subjects must not be pregnant or breast-feeding.
- Female subjects of child-bearing potential with a negative urine pregnancy test and using at least one form of contraception (abstinence allowed).
- Subjects must have a confirmed diagnosis of ARCI-CIE, ARCI-LI, EI or NS (by genotype or willingness to be genotyped).
- Subjects must be clinically judged to be immunocompetent.
- Subjects will have no allergy to secukinumab, latex, or components of the product.
- Subjects will have baseline laboratory testing (normal or non-significant CMP and CBC, and negative for HIV, hepatitis B and C, QuantiFERON®-TB gold)
- Subjects must have an erythema score of at least 18 on IASI and an IASI-E score of 12 (at least moderate severity of erythema) at baseline.

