4.2 Exclusion Criteria

Participants are ineligible for enrollment if they meet any of the following criteria:

- Subjects who are unable to give informed consent or assent.
- Subjects without a confirmed diagnosis of ARCI, EI, or NS.
- Subjects who have a known allergy to secukinumab or latex.
- Female subjects who are pregnant or who are considering becoming pregnant.

Product: Secukinumab

Protocol Number: CAIN457AUS05T

Date: 14 July 2018

20

- Subjects who have prior biologic use targeting IL-17A/IL-17 receptor A or IL-12/IL-23 or who have prior use of TNF-alpha blockers.
- Subjects who have used a systemic retinoid or systemic anti-ichthyosis agent within 4 weeks prior to initiation.
- Subjects who have used topical retinoids or keratolytics within one week prior to initiation.
- Subjects who have used emollient on the area to be biopsied in the previous 24 hours
- Subjects who have a history or diagnosis of inflammatory bowel disease
- Subjects who are on any systemic immunosuppressive agent (i.e. cyclosporine)

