Appendix 1: Schedule of Assessments Flowchart

Phase 1 (double-blind): Visits 1-5;

Crossover: Visit 6

Open label: Visits 7-12

Visit Number	1	2	3	4	5	6	7	8	9	10	11	12
						COW1	OLW1	OLW4	OLW12	OLW20	OLW28	OLW32
	Screen (28 d-21 d of Day 0)	Baseline/ Day 0	Wk 4	Wk 8	Wk 12	Wk 16	Wk 20	Wk 24	Wk 32	Wk 40	Wk 48	Wk 52
Visit Window			±3 days	±3 days	±1 wk	±3 days	±3 days	±1 wk	±1 wk	±1 wk	±1 wk	±1 wk
Consent	X											
Demographics	X											
Inclusion/Exclusion	X	X										
Medical History	X	X	X	X	X	X	X	X	X	X	X	X
Concomitant Meds	X	X	X	X	X	X	X	X	X	X	X	X
AE Assessment	X	X	X	X	X	X	X	X	X	X	X	X
Physical Examination	X	X				X			X			X
Full Skin Examination		X	X	X	X	X	X	X	X	X	X	X
Vital Signs (incl. weight)	X	X	X	X	X	X	X	X	X	X	X	X
Height	X											
Waist circumference		X				X			X			X
Randomization		X										
Saliva Genotyping (if unknown) ²	X											
Buccal swab	X											
Blood Biomarkers	X ¹	X		X		X			X			X
PAX RNA	X ¹	X		X		X			X			X
QuantiFERON®-TB gold	X											X
Hep B/C, HIV testing	X											
Urine HCG(if applicable)	X											X
Chem-20, CBC	X					X			X			X
Lipid panel, glucose, CRP (fasting)		X				X			X			X
Severity evaluations	X	X	X	X	X	X	X	X	X	X	X	X
TEWL		X	X	X	X	X	X	X	X	X	X	X
Tape Strips		X		X		X			X			X
Itch scores		X	X	X	X	X	X	X	X	X	X	X
DLQI and iQoL-32		X				X			X			X
Skin Biopsy (4.5 mm)		X				X			X			X
Photography	X	X	X	X	X	X	X	X	X	X	X	X
Skin Swabs	X	X	X	X	X	X	X	X	X	X	X	X
Injection & Teaching		X										
Dispense study treatment		X	X	X	X	X	X	X	X	X	X	
Review Subject Diary			X	X	X	X	X	X	X	X	X	X

1. To be drawn at screening if the patient is on systemic retinoid
2. At Northwestern only.

Product: Secukinumab

Protocol Number: CAIN457AUS05T

Date: 14 July 2018

All investigators will be trained by [name] before initiation.

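### Section 6.1.7 promises a pregnancy test at baseline, but Appendix 1 schedules it at screening, so the first dose can rest on a test 21 to 28 days old

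*Combined protocol and SAP*

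**What the plan says.** Section 6.1.7 sets the timing: "All female study subjects will be tested for pregnancy at the baseline and end study visits as indicated in Appendix 1". The same section ends with the consequence: "Any woman with a confirmed positive pregnancy test during screening is not eligible for randomization and participation in this study".

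In Appendix 1 the row labelled "Urine HCG(if applicable" (closing bracket omitted here) is marked at Visit 1 (Screen) and Visit 12 (Wk 52) and nowhere else. Section 6.1 gives the interval, "The screening visit is to be performed within 21-28 days of baseline visit [day 0", and its list of screening assessments ends with "skin swabs and scrapings, and pregnancy test (if applicable".

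The eligibility text requires a negative result but sets neither a visit nor a maximum age for it. Section 4.1 reads "Female subjects of child-bearing potential with a negative urine pregnancy test and using at least one form of contraception (abstinence allowed", and section 4.2 excludes "Female subjects who are pregnant or who are considering becoming pregnant". Pregnancy is also on the list in section 5.7 that follows the words "Treatment must be discontinued under the following circumstances". Appendix 1 repeats the inclusion/exclusion check at Visit 2 and places randomization there.

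**The concern.** Section 6.1.7 cites Appendix 1 as its authority, and Appendix 1 shows a different pre-dose visit. The two places cannot both describe the only pre-dose test. The difference matters because the first injection is given on Day 0, three to four weeks after screening.

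If the flowchart governs, eligibility is confirmed again at Visit 2, with pregnancy among the exclusions, but no test is scheduled there to support that confirmation. A woman in very early pregnancy at screening, or one who conceived between screening and Day 0, could be randomized and dosed. The plan requires treatment to stop when a pregnancy is found (5.7) and the pregnancy to be reported to the DSMB within 24 hours of learning of it (7.4). It would be consistent to look for pregnancy immediately before exposure. With two sites working from one protocol, there is also a risk that one tests on Day 0 and the other does not.

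**Working it through.** The check is a cross-reading plus day arithmetic. The plan gives no figure of its own to reproduce.

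**1. Where each place puts the pre-dose test**

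| Place | Pre-dose test | Later test |
|---|---|---|
| 6.1.7, first sentence | Baseline visit | End of study |
| 6.1.7, last sentence | Refers to a positive test during screening | none stated |
| 6.1 | Screening visit | not addressed |
| Appendix 1, urine HCG row | Visit 1 (Screen); Visit 2 empty | Visit 12 (Wk 52) |
| 4.1 | Negative test required, no visit given | not addressed |

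No other section schedules a Day 0 test.

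**2. Is the Appendix 1 row read correctly?** The row has the same two-mark pattern as the QuantiFERON row, and section 6.1.6 confirms QuantiFERON at Visit 1. Rows that start at baseline, such as TEWL, tape strips and waist circumference, keep an empty first cell. Section 6.1 independently places the pregnancy test at screening. The marks therefore fall at Visits 1 and 12.

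**3. Age of the last scheduled test at first dose**

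- Screening: day -28 to day -21 (6.1 and the Appendix 1 header).
- First dose: Day 0 (5.2.1 and 5.2.2).
- Age = day of first dose minus day of test.
- Under Appendix 1 and 6.1: 0 - (-21) = 21 days at the least and 0 - (-28) = 28 days at the most.
- Under the first sentence of 6.1.7 read literally: 0 - 0 = 0 days.

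**4. Exposure before the next scheduled test.** After Visit 1 the next marked HCG is Week 52. Under section 3.4.2, injections fall at Weeks 0, 1, 2, 3 and 4, so a woman on secukinumab would be due five 300 mg doses by Week 4.

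**5. Cost of adding the test.** Extra tests = 1 × number of applicable women. The documents do not give that number. With 40 randomized the range is 0 to 40. If half of the subjects are assumed to qualify, it is 1 × 20 = 20.

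**The case against.** The strongest reply is that the sections can be read together. Section 6.1 lists a test at screening without saying that it is the only one, and 6.1.7 says that women will be tested at baseline. A site that follows both tests twice before dosing, and the defect shrinks to a missing mark in the flowchart. This stands in part: the stale-test scenario arises only where Appendix 1 is followed over the text. It also means that a Day 0 test is already promised, so adding the mark reconciles the documents and does not add a new procedure.

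A second reply is that baseline in 6.1.7 loosely means the screening work-up, since much of what 4.1 calls baseline laboratory testing is done at Visit 1. That is possible, although several sections tie the baseline visit to day 0 and Appendix 1 gives the two visits separate columns. On that reading 6.1.7 is misworded and no Day 0 test is scheduled at all, so a correction is needed either way.

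Third, a woman who tested positive on Day 0 would already be ineligible under 4.1 and 4.2, and 3.4.1 describes screening as a period of three to four weeks, so 6.1.7 need not be confined to Visit 1. This is right. An explicit bar after a positive baseline test is a clarification and does not close a separate gap.

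Finally, contraception, the exclusion of women considering pregnancy, and the Visit 2 eligibility and history review all lower the risk, and the documents give no basis for estimating what remains. That is accepted, and no rate is claimed here.

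**Conclusion.** The inconsistency is real. Under Appendix 1 and section 6.1 the last scheduled pregnancy test is 21 to 28 days old at first dose; under section 6.1.7 read literally it is 0 days old. The conclusion about dosing assumes that a site works from the flowchart. Which reading was intended cannot be settled from the documents, but both call for an amendment.

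This is a matter of participant safety and of the two sites acting alike. It has no bearing on the primary endpoint, blinding or the efficacy analysis. It should be corrected. The mismatch and the day count are certain, while the probability that a pregnancy would be missed is unknown.

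**What to change.** Keep the screening test and add a mark for urine HCG at Visit 2 (Baseline/Day 0) in Appendix 1.

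Reword 6.1.7 to say that women of child-bearing potential are tested at screening, at baseline before randomization and the first dose, and at end of study, and that a positive result at either pre-dose test bars randomization and dosing. This wording also settles a second mismatch that the amendment should name: 6.1.7 covers every female subject, whereas 6.1 and Appendix 1 limit the test to those for whom it applies.

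The cost is one added mark, two sentences, and one urine test per applicable woman at a clinic visit already planned.

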6.1.8 Complete Blood Count and Clinical Chemistry Testing

A blood draw by a trained phlebotomist at visits 1, 2, 4, 6, 9, and 12 as indicated in Appendix 1. As per the schedule, hemoglobin, hematocrit, platelet count and white blood cell count with differential will be measured. Additionally, hepatic transaminases, blood urea nitrogen, creatinine, sodium, potassium, chloride, bicarbonate and glucose will be measured. At visits 2, 4, 6, 9, and 12 fasting lipids, glucose and C-reactive protein (CRP) will be measured.

6.1.9 Severity Evaluations (Appendices 2-6, 9, 10)

Severity evaluations will be performed at every study visit. Severity assessments will be performed by: Ichthyosis Area and Severity Index (IASI), Congenital Ichthyosis Severity Instrument (CISI), a modified CISI (m-CISI), the Bodemer scoring system (Bodemer et al 2011), and the Yale Ichthyosis Severity

Product: Secukinumab

Protocol Number: CAIN457AUS05T

Date: 14 July 2018

27

Index. CISI is a validated score that assesses individual scores for erythema, scaling and alopecia, but is limited in that it is not a single score, includes a feature found in the minority of patients (alopecia) and includes non-uniform Likert scales (0-4+ or 0-5+). M-CISI eliminates the alopecia score, adopts a 5-point Likert for erythema and scaling, and averages the erythema and scaling scores for a single global assessment; it is a new scale that is being validated herein but will not be used for endpoints. IASI is a composite score based on the global CISI score that captures differences in severity in different body regions as a function of their body surface area and also standardizes the number of choices within the Likert scales for erythema and scaling. As in the EASI score for AD and the PASI score for psoriasis, IASI evaluates erythema and scaling as 0-4+ in severity at each of 4 locations: head and neck (including scalp); arms (including palms); legs (including soles); and trunk, prorated based on body surface area in these sites and the percentage of involvement in each of these sites (total possible score for each is 24 and total composite score is 48). To include a patient-reported severity score, we will use the Congenital Ichthyosis Severity Index, which has been validated for patient use (Kamalpour et al 2010), and the m-CISI. We will also pilot in the US a complex, non-validated burden of disease scoring system proposed by Bodemer et al in France, which heavily weighs associated morbidity (contractures, ectropion, mouth tightness, fissures) in addition to other measures of severity. All investigators/ sub-investigators will be trained based on photographs before study initiation to uniformly assign CISI, m-CISI, Bodemer, and IASI scores. A huge issue is the paucity of validated scores for ichthyosis severity. Our evaluations will be performed concurrently (but without conferring) by two investigators to allow inter-rater reliability, as well as at screening and again at baseline (at 3-4 weeks to minimize recall bias) for assessing test-retest reliability. As such, we hope to use this opportunity to assess reliability in these un-validated instruments. Patient-reported itch will be quantified on a 0-10 numerical rating scale (NRS) and by 5-D itch score (Elman et al 2009); a 1-10 score pain assessment is part of the Bodemer scale. The Yale Severity Index was recently developed and tested at a recent meeting of the Foundation for Ichthyosis and Related Skin Types. It includes a 0-4+ scale for erythema and for scaling, and provides pictorial representations for comparison, dividing scaling into lamellar and keratoderma scale scores. This study is the first time it will be applied to patients in an investigation.
